3.3.4 EORTC QLQ-C30

Patients are to complete the EORTC QLQ-C30 as per the schedule of events.

QLQ-C30 comprises 30 questions on daily quality of life, with each question having a response score on a scale of 1-4 or 1-7. QLQ-C30 incorporates a global health status, five functional scales (physical, role, cognitive, emotional and social), three symptom scales (fatigue, nausea/vomiting, pain), and six single items (dyspnoea, insomnia, appetite loss, constipation, diarrhoea, financial difficulties). Each scale and single item is derived and scaled to fall in the range 0 to 100, where a high score represents higher response. Table lists the scores to be derived and the items used in their derivation.

Table 1: QLQ-C30 Scales

Derived Scale	Scale	Items	#Items	Range
Global health status	QL	29, 30	2	6
Functional scale – Physical Functioning	PF	1, 2, 3, 4, 5	5	3
Functional scale – Role Functioning	RF	6, 7	2	3
Functional scale – Emotional Functioning	EF	21, 22, 23, 24	4	3
Functional scale – Cognitive Functioning	CF	20, 25	2	3
Functional scale – Social Functioning	SF	26, 27	2	3
Symptom scale – Fatigue	FA	10, 12, 18	3	3
Symptom scale – Nausea and Vomiting	NV	14, 15	2	3
Symptom scale – Pain	PA	9, 19	2	3
Symptom item – Dyspnoea	DY	8	1	3
Symptom item – Insomnia	SL	11	1	3
Symptom item – Appetite Loss	AP	13	1	3
Symptom item – Constipation	CO	16	1	3
Symptom item – Diarrhoea	DI	17	1	3
Symptom item – Financial Difficulties	FI	28	1	3

The following algorithm will be used in deriving the functional and symptom scale scores:

1. Derive the raw score (RS) for each functional and symptom score by deriving the average of the contributing items (I).

$$RS = (I_1 + I_2 + \dots + I_n)/n$$

2. Derive the standardised score (Score) for each functional and symptom score by mapping the raw score to the range from 0 to 100, where a higher score represents a better level of function or a worse level of symptoms.

For Function scales:

$$Score = \{1 - (RS-1)/range\} \times 100$$

For Symptom scales and Global health status:

$$Score = \{(RS-1)/range\} \times 100$$

3. For derived scales that include two or more items, a derived value will be calculated if at least half of the items are non-missing. If more than half of the items are missing then the scale will be set to missing.

For each of the standardised function scales, symptom scales, global health status scale and standardised single item scales the Baseline for each patient is parent trial baseline. The absolute change from the parent trial Baseline to each subsequent assessment will be derived for each of the standardised scales and standardised single item scores.

Changes in the global health status will be identified as adverse if the score has decreased (negative absolute change from the parent trial Baseline) in a 3-month time period.

Patients with no adverse change at each 3-month time period since the start of the study will be identified.

3.3.5 *EQ-5D-5L*

Patients were to complete the EQ-5D-5L as per the schedule of events .

EQ-5D-5L comprises 5 questions (mobility, self-care, usual activities, pain/discomfort, anxiety/depression), each with five levels plus the EQ Visual Analogue scale. The patient response to each of the 5 questions will be mapped to the score indicated in Table 2. The five mapped responses, also known as the 5L profile, will then be used to obtain a normalised score for each patient assessment by obtaining the country-specific normalised value from the Crosswalk Index Value Calculator.

Table 2: EQ-5D-5L Response Scores

Question	Response	Score
Q1: Mobility	I have no problems in walking	1
	I have slight problems in walking	2
	I have moderate problems in walking	3
	I have severe problems in walking	4
	I am unable to walk	5
Q2: Self-Care	I have no problems washing or dressing myself	1
	I have slight problems washing or dressing myself	2
	I have moderate problems washing or dressing myself	3
	I have severe problems washing or dressing myself	4
	I am unable to wash or dress myself	5
Q3: Usual Activities	I have no problems doing my usual activities	1
	I have slight problems doing my usual activities	2
	I have moderate problems doing my usual activities	3
	I have severe problems doing my usual activities	4
	I am unable to do my usual activities	5
Q4: Pain/Discomfort	I have no pain or discomfort	1
	I have slight pain or discomfort	2
	I have moderate pain or discomfort	3
	I have severe pain or discomfort	4
	I have extreme pain or discomfort	5
Q5: Anxiety/Depression	I am not anxious or depressed	1
	I am slightly anxious or depressed	2
	I am moderately anxious or depressed	3
	I am severely anxious or depressed	4
	I am extremely anxious or depressed	5

The absolute change from the Parent trial baseline to each subsequent assessment will be derived.

Changes in the normalised score will be identified as adverse if the score has decreased (negative absolute change from the parent trial Baseline) in a 3-month time period.

Patients with no adverse change at each 3-month time period since the start of the study will be identified.

3.3.6 *FACIT-F*

The FACIT-F (functional assessment of chronic illness therapy - fatigue) version 4 comprises 41 items measuring an individual's level of fatigue during their usual daily activities. The level of fatigue is measured on 5 subscales (Physical Well-Being subscale, Social/Family Well-Being subscale, Emotional Well-Being subscale, Functional Well-Being subscale and additional concerns).

Where applicable, item variables will be reverse coded for the purpose of generating the scale scores as per the FACIT-F scoring guidelines. For each patient, at each visit, the FACT-G Total Score, FACIT-F Total Score and FACIT-F Trial Outcome Index will be calculated. For guidelines on handling missing data and scoring options, the administration and scoring guidelines in the manual or on-line at www.facit.org will be used.

Changes in the FACIT-F Total score will be identified as adverse if the score has decreased (negative absolute change from Baseline) in a 3-month time period.

Patients with no adverse change at each 3-month time period since the start of the study will be identified.

Where possible, the change from the Parent Baseline may also be described. Parent trials AK580, AK585 and AK578 used version 4 of the FACIT questionnaire, while AK579 did not collect this data.

3.3.7 *Self-Injection Questionnaire*

Patients will complete a non-validated questionnaire at every visit to determine whether self-injection by patients is well-accepted and the support provided sufficient. Each question was to be answered using one of the available categorical scores.

No derivations will be performed on this data. This data will only be listed.

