3.2. Endpoints

3.2.1. *Safety & Efficacy Endpoints:*

Primary:

- Long term safety of rVA576 (Coversin) therapy as assessed by AEs, serious adverse events (SAEs), vital signs, results of standard laboratory tests (clinical chemistry, haematology and urinalysis), and results of electrocardiograms (ECGs).

PNH Secondary:

1. Proportion of subjects with thrombotic and haemolytic event-free status during each 3 month time period since the start of the study.
2. Time to thrombotic or haemolytic event since the start of the study.
3. Proportion of subjects who require PRBC transfusion during each 3-month period since the start of the study and over the entire period of the study, with analysis of i) subjects who were transfusion-dependent when they started receiving rVA576 (Coversin), ii) subjects who were transfusion-independent when they started receiving rVA576 (Coversin), and iii) all subjects, and further stratification of these proportions by a) patients who were complement inhibitor-naïve prior to treatment with rVA576 (Coversin), and b) patients who received treatment with another complement inhibitor before switching to rVA576 (Coversin).
4. Time to first transfusion since joining the study.
5. Proportion of subjects with no adverse change in overall scores of Quality of Life using the EORTC QLQ-C30, the EQ-5D-5L and FACIT-F instruments at each 3-month time period since the start of the study.
6. Proportion of subjects with serum Lactate Dehydrogenase (LDH) ≤ 1.8 , >1.8 to 2.4, >2.4 to 3, and >3 times the upper limit of normal (ULN) at each 3-month time period since the start of the study.

7. Proportion of subjects with median serum Lactate Dehydrogenase (LDH) ≤ 1.8 , >1.8 to 2.4 , >2.4 to 3 , and >3 times the upper limit of normal (ULN) over the entire duration of the study.
8. Proportion of transfusion-independent subjects at each 3-month time point, with haemoglobin (g/L) above the baseline haemoglobin value they had at the start of the trial from which they entered CONSERVE. With baseline for CAPSTONE (AK580) defined as the haemoglobin value at which they received their qualifying transfusion (the set point) or for COBALT (AK579) and CONSENT (AK578) the haemoglobin value at which patients entered those trials. With separate analysis of subjects who were i) transfusion-independent prior to receiving rVA576 (Coversin) and remain transfusion-independent and ii) transfusion-dependent prior to receiving rVA576 (Coversin).

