3.1 Baseline (study entry) and Parent trial Baseline

In order to describe changes over time, and compare values to the pre-Coversin dosing value (historical baseline), some parameters (LDH, CH50, quality of life scores, haemoglobin) may have both parent trial baseline values and CONSERVE baseline values used in analyses. To avoid any confusion the term “baseline” will always refer to CONSERVE baseline, while ‘Parent trial baseline’ will be used otherwise.

Baseline will therefore be defined as the last measurement prior to CONSERVE study entry.

Parent trial baseline will be defined as :

- Baseline for CAPSTONE (AK580) defined as the value at which they received their qualifying transfusion (the set point)
- Baseline for COBALT (AK579) or CONSENT (AK578) the value at which patients entered those trials.

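### Any fall in a quality-of-life score counts as adverse change, and the three instruments use different baselines, so the endpoint 5 proportion has no reference value for maintained quality of life

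*SAP*

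**What the plan says.** Secondary endpoint 5 (protocol 3.2.1, repeated in SAP 2.4.2) is the "Proportion of subjects with no adverse change in overall scores of Quality of Life" on three instruments by 3-month period. The protocol does not define adverse change. The SAP does:

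- SAP 3.3.4, QLQ-C30: "Changes in the global health status will be identified as adverse if the score has decreased (negative absolute change from the parent trial Baseline".
- SAP 3.3.5, EQ-5D-5L: "Changes in the normalised score will be identified as adverse if the score has decreased (negative absolute change from the parent trial Baseline".
- SAP 3.3.6, FACIT-F: changes in the Total score "will be identified as adverse if the score has decreased (negative absolute change from Baseline) in a 3-month time period".

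None of the three sets a minimum size, and an unchanged score is not adverse. SAP 3.1 says that "the term “baseline” will always refer to CONSERVE baseline, while ‘Parent trial baseline’ will be used otherwise". FACIT-F is therefore judged against entry to CONSERVE, and the other two against the value before Coversin. SAP 4.11.5 to 4.11.7 tabulate the proportion and also summarise observed values and change from baseline at each visit. Protocol Table 8 schedules the questionnaires at entry, at months 1, 2 and 3, and then every 3 months.

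**The concern.** One aim of the study is to show that the effect seen in the parent trial persists. A patient whose quality of life is constant still scores slightly differently from one questionnaire to the next. With the cut at zero, many such patients fall on the adverse side by chance.

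There is no concurrent control and no target proportion, so a reader has nothing to compare the figure with. A FACIT-F result of about half with no adverse change could be read as widespread deterioration when it is what full stability would produce. On QLQ-C30 and EQ-5D-5L the error can run the other way: a patient who improved in the parent trial can lose part of that gain during CONSERVE and still count as having no adverse change. One endpoint thus holds three proportions that do not mean the same thing.

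**Working it through.** The documents give no expected proportion, reliability or important difference, so there is no figure of the plan's to reproduce. The check starts from the rule itself.

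**Step 1: one visit, no true change.** If visit errors are symmetric and exchangeable, a fall is as likely as a rise, so

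P(flagged) = (1 - P(tie)) / 2.

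The ceiling is one half, approached when ties are rare. Ties depend on how fine the score is:

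- FACIT-F Total: 41 items (SAP 3.3.6), so a fine scale.
- QLQ-C30 global health: 2 items with range 6 (SAP 3.3.4, Table 1). One category on one item moves the score by (1/2)/6 x 100 = 8.33 points, giving 13 levels.
- EQ-5D-5L: 5 items with 5 levels (SAP 3.3.5) and a no-problems ceiling.

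**Step 2: size of P(tie).** This was simulated with rounding to the scale step and clipping at floor and ceiling. The assumptions, none of them from the documents, are:

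- FACIT-F: range 0-160, step 1, between-patient SD 20, means 100 and 120 (mid-range) or 145 (near the ceiling), error SD 2-10 per visit.
- QLQ-C30: means 55-85, SD 20, error SD 3-12.
- EQ-5D-5L: sum of item levels as a stand-in for the index, item error SD 0.1-0.5 level.

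| Score | Ties | Flagged at one visit | Flagged if any of months 1, 2, 3 counts |
|---|---|---|---|
| FACIT-F, mid-range | 3-16% | 42-49% | 67-74% |
| FACIT-F, near ceiling | 20-33% | 34-40% | 54-65% |
| QLQ-C30 global health | 21-69% | 15-40% | 28-65% |
| EQ-5D-5L | 23-76% | 12-38% | 22-63% |

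Example: FACIT-F with mean 100 and error SD 2 has 13.9% ties, and (1 - 0.139)/2 = 43%.

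**Step 3: three visits in one period.** Without ties, a stable patient escapes the flag only if baseline is the lowest of four exchangeable values. That has probability 1/4, so 3/4 are flagged. Later periods hold one scheduled visit and stay at one half or below.

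**Step 4: parent trial baseline.** Let a patient gain d SDs of change in the parent trial and then stay stable. Before ties, P(flagged) = Phi(-d):

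- d = 0.5 gives 31%.
- d = 1 gives 16%.

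The QLQ-C30 and EQ-5D-5L shares in the table therefore apply before any parent-trial gain.

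**Step 5: information left in the proportion.** A true decline of 0.5 SD of change raises the flagged share, before ties, from 50% to Phi(0.5) = 69%. The proportion does respond to decline. With 25 of 50 patients flagged, the exact 95% interval is 36-64%. Fifty is the upper planned number, and with 10 of 20 the interval is 27-73%.

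**Step 6: effect of a threshold.** With a cut of 0.5 between-patient SD and reliability r, P(flagged | stable) = Phi(-0.5 / sqrt(2(1 - r))). This gives 29% at r = 0.6 and 13% at r = 0.9. Simulation on FACIT-F with one-point rounding gives about 13-28%.

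**The case against.** The strongest reply is that everything here is descriptive. This is one of twelve secondary endpoints, the primary endpoint is safety, and no decision or target hangs on the proportion. No decrease is objective and prespecified, and any threshold makes the result look better. This stands as a limit on severity. It does not give the reader a reference value.

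A reader might also infer four stronger things that the documents do not support:

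- **That about half of stable patients are flagged on every instrument.** That holds only for FACIT-F away from the ceiling. Ties are common on the other two scores. Their comparator is also a pre-treatment value, and entrants must be judged to be benefiting (inclusion criterion 2), so exchangeability need not hold.
- **That the analysis cannot show maintenance.** SAP 4.11.5 to 4.11.7 summarise change at each visit, individual scores are listed, and step 5 shows that the proportion carries some information.
- **That the first period certainly has three chances to fail.** SAP 3.3.4 to 3.3.6 speak both of a fall within a period and of status at each period, and protocol 9.1 reports by 3-month time point. A single month-3 assessment is a fair reading. The text is ambiguous, and the artefact is only possible.
- **That 0.5 SD is the correct cut.** The documents give no basis for it, and it still flags some stable patients.

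**Conclusion.** The concern holds in limited form. The adverse-change rule has no minimum size for any of the three instruments. On FACIT-F Total it would flag roughly 40-50% of stable patients per visit (34-40% near the ceiling), and on QLQ-C30 global health and EQ-5D-5L about 12-40% before any parent-trial gain. If all visits in a period count, the first period could reach about 75% on FACIT-F for mechanical reasons, and the figure would then seem to improve.

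The one-half ceiling per visit needs only exchangeable visits. The ranges below it rest on the assumed error SDs, means and scale limits. They also take the SAP's 41-item FACIT-F, whereas protocol 5.12 describes a 13-item fatigue scale.

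The endpoint 5 proportion therefore cannot be read on its own as maintained or lost. The visit summaries reduce the harm. This should be fixed, at low cost, but it does not threaten the trial's main conclusions.

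**What to change.** Before database lock, amend SAP 3.3.4 to 3.3.6:

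1. Define adverse change as a fall at or beyond a justified threshold for each instrument, tied to the exact score used, and report improved, stable and worsened.
2. Use one visit per period, the period-end visit (month 3 for period 1).
3. State one baseline for this endpoint on all three instruments. CONSERVE baseline fits a question about maintenance. Add parent trial baseline as a supplementary row where it was collected (SAP 3.3.6 says AK579 has no FACIT-F data). Align SAP 4.11.5 to 4.11.7, whose unqualified baseline means CONSERVE baseline under SAP 3.1.
4. Keep any decrease as a sensitivity row, with a footnote giving the share expected by chance in stable patients.

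The cost is SAP text and a few derivations, with no new data. The downsides are that each threshold needs a justification, some stable patients are still flagged, and the proportion will look more favourable. The study is open-label and the sponsor may review accruing data (SAP 4.13), so a threshold chosen after seeing the results would not be credible.

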3.4 Safety Measurements and Variables

3.4.1 *Major Adverse Vascular Event (MAVE) Assessment*

The MAVE will be used to collect information on large and small vessel thrombosis as well as micro thrombosis and will be recorded always pre-dose at each clinic visit.

MAVE will be recorded as part of the AEs and the following details will be reported:

- MAVE location:

- Limbs
 - Lungs
 - Brain
 - Heart
 - Kidneys
 - Intestines
 - Liver
 - Other
- Method of diagnosis:
 - MRI
 - Ultrasound
 - Angiogram
 - Other

3.4.2 Thrombotic and Haemolytic Events

Thrombotic and Haemolytic Events will include, but are not limited to, the following: haemolytic anaemia, thrombocytopenia, red blood cell hemolysis indicated by dark urine, Budd-Chiara syndrome, any other thrombotic or hemolytic event deemed to be associated with PNH.

A haemolytic event will be defined as a rise in LDH or other biochemical evidence of haemolysis (eg increasing serum bilirubin or liver enzymes) accompanied by an increase in symptoms (eg myalgia, erectile dysfunction, fatigue) and/or frank haemoglobinuria. Increased symptoms without objective haematological or biochemical evidence of haemolysis will not be counted as haemolytic events.

In addition, the following signs and symptoms may be reviewed and classified as Thrombotic/Haemolytic events if appropriate:

- Acute kidney failure
- Hypertension
- Myocardial infarction
- Stroke
- Lung complications (e.g. Pulmonary embolism)
- Pancreatitis
- Liver necrosis
- Encephalopathy (brain dysfunction)
- Seizure
- Coma
- Premature death (secondary to neurologic, cardiac, kidney, and gastrointestinal organ dysfunction)

3.4.3 Adverse Events (AEs)

All AEs, which occurred at any time after signing the informed consent form (ICF), will be recorded in the electronic Case Report Form (eCRF). The following details will be reported for each adverse event:

- Start and stop dates
- Severity, using CTCAE grading 1 to 5
- Relationship to study treatment:
 - Unrelated
 - Possibly Related
 - Related
- Serious:
 - Yes
 - No
- Action taken with study treatment:
 - Dose increased
 - Dose not changed
 - Dose reduced
 - Drug interrupted
 - Drug withdrawn
 - Not applicable
 - Unknown
 - Other
- Outcome
 - Fatal
 - Not recovered/not resolved
 - Recovered/resolved
 - Recovered/resolved with sequelae
 - Recovering/resolving
 - Unknown

Other action taken, whether the AE caused discontinuation, details of death, hospitalisation, last dose before the event and other information related to the AE will be collected and listed.

Treatment emergent adverse events are defined as any AE with a recorded start date/time on or after the date/time of start of study medication. All patients enrolled into the CONSERVE study will have transitioned from a parent clinical trial and all will have been previously treated with rVA576, therefore all AEs recorded under protocol AK581 will be considered treatment-emergent.

3.4.4 Safety Clinical Laboratory Measurements

A blood and urine sample will be collected for clinical laboratory measurements (haematology, biochemistry and urinalysis) as per the schedule of events. The following laboratory parameters for haematology, chemistry and urinalysis will be evaluated at each clinical site's local laboratory:

Haematology

- Haemoglobin [g/L]

- Haematocrit [%]
- Mean cell haemoglobin [pg]
- Mean cell haemoglobin concentration [g/L]
- Mean cell volume [fL]
- Red blood cell count [$10^{12}/L$]
- Erythrocyte sedimentation rate [mm/h]
- Platelets [$10^9/L$]
- White blood cell count [$10^9/L$]
- Neutrophils absolute [$10^9/L$]
- Lymphocytes absolute [$10^9/L$]
- Monocytes absolute [$10^9/L$]
- Eosinophils absolute [$10^9/L$]
- Basophils absolute [$10^9/L$]
- Reticulocytes [$10^9/L$]

Chemistry

- Lactate dehydrogenase [U/L]
- Sodium [mmol/L]
- Potassium [mmol/L]
- Bicarbonate [mmol/L]
- Urea [mmol/L]
- Creatinine [μ mol/L]
- Chloride [mmol/L]
- Albumin [g/L]
- Calcium [mmol/L]
- Gamma-glutamyl transpeptidase [U/L]
- Glucose (random) [mmol/L]
- Alkaline phosphatase [U/L]
- Alanine aminotransferase [U/L]
- Aspartate aminotransferase [U/L]
- Creatine kinase [U/L]
- Total Bilirubin [μ mol/L]
- Bilirubin (Direct) (only if Total is elevated) [μ mol/L]
- Phosphate (Inorganic) [mmol/L]
- Protein (Total) [g/L]

For each of the haematology and chemistry parameters, values from the locally reported laboratory will be converted to the standardised units shown in parenthesis during statistical programming of the SDTM datasets.

Urinalysis

- Leukocytes
- Protein
- Bilirubin
- Glucose
- pH
- Ketones

- Nitrates
- Blood
- hCG (female patients)
- Specific gravity

At the discretion of the Investigator:

- Microbiology
- Urine microscopy
- Pregnancy testing
- Urobilinogen

Central Laboratory Testing

The following parameters may also be evaluated at the Central Laboratory but are not mandatory:

- LTB4
- Total LDH and LDH Isoenzyme
- Total bound and unbound C5

Out-of-range laboratory data will be flagged as low or high according to gender and laboratory specific normal ranges.

The absolute change from Baseline to each subsequent assessment will be derived for each of the continuous laboratory parameters.

Haemoglobin

For Haemoglobin, the Parent trial baseline will be used. Patients with an haemoglobin above the baseline haemoglobin value they had in the parent trial will be flagged.

The mean haemoglobin value post study entry will be calculated for each patient.

